4.2 Power/Sample Size

Statistical hypothesis

With regard to the stroke incidence the formal statistical hypothesis between any two groups is as follows:

$$H_0 : HR = \text{Incidence}_1 / \text{Incidence}_2 = 1$$

against the alternative,

$$H_1 : HR = \text{Incidence}_1 / \text{Incidence}_2 \neq 1$$

Where HR denotes the hazard ratio, Incidence_1 is the stroke incidence rate for example in the treatment group 1 (eg, INR level below 2.0) and Incidence_2 is the stroke incidence rate in the treatment group 2 (INR level 2.0-3.0 used as the reference group).

Similar hypotheses apply for the comparisons between the other outcomes and INR targets and the TTR levels.

Power calculations

According to Wallentin¹⁴ for AF patients using warfarin the incidence rates for “stroke and systemic embolism” vary from 1.34 to 2.06 events per 100 patient years depending on the mean TTR values in different centers. For “major bleeding” events the incidence ranges from 3.11 to 4.13 and for “total bleeding” from 16.56 to 18.96. For “total death” the incidence rates vary from 3.04 to 5.72 per 100 patient years. Thus we perform power calculations for incidence rates 1.5, 3, and 6 and consider differences from of 5 % to 50% by 5% increments or equivalently relative risks from 1.05 to 1.50.

The population size in the areas participating in the study is about 3 million. About 1.6 % of the population are warfarin users and out of these about 67% are AF patients¹⁵ resulting in a study population of size 32 000. Assuming a 3-year mean follow-up time this results in 96 000 person years. According to Helin *et al.*⁸ the proportion on INR measurements in the categories: under 2.0, 2.0-3.0, and over 3.0 are 21.7 %, 63.6 % and 14.7 % respectively. In person time this means 21000 (INR under 2.0), 61000 (INR 2.0-3.0) and 14000 (INR over 3.0) person years. The power calculations are performed for the comparisons between the INR categories 2.0–3.0 as the reference group against the INR category below 2.0. Because some of the patients may not have INR measurements available we also repeat the calculations for a 20% smaller study population size. The resulting calculations are given in Table 4.2-1.

Table 4.2-1: Power (%) for comparisons between group 1 (INR below 2.0) and group 2 (INR values 2.0-3.0 used as the reference group) for different relative risk values, incidence rates and study population sizes.

Relative risk	Incidence rate per 100 patient years		
Study population size = 32 000			
	1.5	3.0	6.0
1.05	11.7	19.0	35.0
1.10	30.8	55.2	86.2
1.15	56.5	86.1	99.3
1.20	78.6	97.6	100
1.25	91.7	99.8	100
1.30	97.4	100	100
Study population size = 80% × 32 000 = 25 600			
	1.5	3.0	6.0
1.05	10.3	16.1	29.1

Table 4.2-1: Power (%) for comparisons between group 1 (INR below 2.0) and group 2 (INR values 2.0-3.0 used as the reference group) for different relative risk values, incidence rates and study population sizes.

Relative risk	Incidence rate per 100 patient years		
1.10	25.6	46.4	77.8
1.15	47.6	77.7	97.8
1.20	69.2	94.1	99.0
1.25	84.9	99.0	100
1.30	93.8	99.9	100

According to the power calculations the current study will be able to detect 20%, 15% and 10% differences in endpoints with incidences rates of 1.5, 3.0 and 6.0 per 100 person years with sufficient power of about 80% or higher, respectively.

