- Index date is defined as the date of first purchase of warfarin after 01-Jan-2007. Follow-up of the patients starts on the index date, and ends on 31-Dec-2011, at time of death or at time of emigration whichever occurs first. Treatment and comorbidity history is gathered from the period 01-Jan-2005 and 31-Dec-2006.

Data Analyses: Stratified incidence rates with 95% CIs will be estimated for each endpoint within the strata of the INR levels, time in therapeutic INR range (TTR) categories, and other covariates.

The crude and adjusted hazard ratio (HR) estimates with 95% CIs and P-values will be estimated within the INR levels and TTR categories using the conventional Cox's proportional hazards model adjusting for other covariates. For INR the category 2.0–3.0 will be used as the reference category. Similarly for TTR the category $\geq 60\%$ of time will be used as the reference category.

Sample Size/Power: According to the power calculations we are able to detect 10-20% differences in the main endpoints with sufficient power of approximately 80% or higher.

Limitations/Strengths:

- No exact prescribed dosages are available. Warfarin exposure is assumed based on the information of purchases and package sizes with defined daily doses (DDDs).
- Fully reliable information on eg, acetylsalicylic acid use is not available because the data of the prescription register exclude relatively inexpensive packages and over the counter medications which are not reimbursed.
- Medications used during hospitalizations are not available. However, based on the hospital care register the hospitalization periods can be taken into account to define gaps in the drug treatment periods.
- The laboratory data are collected from separate local central laboratories. Changes in places of domicile may affect the follow-up of the patients. On the other hand, previous published surveys on the subject have not included INR follow-up to this extent.

TABLE OF CONTENTS

TITLE PAGE	1
SYNOPSIS.....	3
TABLE OF CONTENTS.....	5
1 INTRODUCTION	7
1.1 Study Rationale.....	7
1.2 Research Question	7
2 OBJECTIVES.....	8
2.1 Primary Objectives.....	8
2.2 Secondary Objectives.....	8
2.3 Exploratory Objectives	8
3 STUDY DESIGN.....	8
3.1 Overview of Study Design.....	8
3.2 Study Population.....	9
3.2.1 Inclusion Criteria.....	9
3.2.2 Exclusion Criteria.....	9
3.3 Data Source/Data Collection Process	9
3.4 Definitions of Study Variables.....	11
3.4.1 Outcomes/Endpoint Variables	11

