2 OBJECTIVES

2.1 Primary Objectives

- 1) To investigate and compare risk of stroke, systemic thromboembolic events, and myocardial infarction among AF patients in relation to INR levels: under 2.0, 2.0-3.0, and over 3.0.
- 2) To investigate and compare risk of bleeding events among AF patients in relation to INR levels: under 2.0, 2.0-3.0, and over 3.0.
- 3) To investigate and compare mortality risk among AF patients in relation to INR levels: under 2.0, 2.0-3.0, and over 3.0.

The primary objectives are evaluated separately for prevalent users of warfarin and for new users of warfarin.

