4.1.1 Primary Objective

Objectives 1-3: Stratified incidence rates with 95% confidence intervals (CIs) will be estimated for each primary endpoint within the strata of the exposure variables (INR levels and TTR categories) and other covariates, including history of AF prior the index date.

The crude and adjusted hazard ratio (HR) estimates with 95% CIs and P-values will be estimated separately within the INR levels and TTR categories using the conventional Cox's proportional hazards model adjusting for other covariates. For INR the category 2.0–3.0 will be used as the reference category. Similarly for TTR the category $\geq 60\%$ of time will be used as the reference category.

The objectives will be evaluated separately for the prevalent warfarin user population and the new warfarin user population. The new warfarin user population consists of those patients who initiate warfarin treatment during the follow-up (01-Jan-2007 to 31-Dec-2009).

A further sensitivity analysis will be performed where the adjusted HRs are estimated stratifying by the history of AF prior to the index date.

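### The power of about 80% or higher holds only for INR below 2.0 versus 2.0–3.0 in the pooled cohort of 32 000, yet section 4.2 and the Synopsis state it for the study as a whole

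*Protocol*

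**What the plan says.** The concluding paragraph of Protocol section 4.2 says that "the current study will be able to detect 20%, 15% and 10% differences in endpoints" with rates of 1.5, 3.0 and 6.0 per 100 person-years, "with sufficient power of about 80% or higher, respectively". It names neither the population size nor the INR comparison. The Synopsis (Sample Size/Power) is broader: "we are able to detect 10-20% differences in the main endpoints with sufficient power of approximately 80% or higher", with no rate, comparison or population attached.

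The calculation behind this covers one contrast, INR below 2.0 against 2.0–3.0, in the whole cohort. The person-time is given for all three INR levels: "In person time this means 21000 (INR under 2.0), 61000 (INR 2.0-3.0) and 14000 (INR over 3.0) person years". Two population sizes are tabulated, the second for this reason: "Because some of the patients may not have INR measurements available we also repeat the calculations for a 20% smaller study population size".

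All three primary objectives in section 2.1 compare INR above 3.0 as well as INR below 2.0, and the section adds: "The primary objectives are evaluated separately for prevalent users of warfarin and for new users of warfarin". Section 4.1.1 repeats the separate evaluation. The lowest tabulated rate, 1.5, follows from a cited composite of stroke and systemic embolism whose rates "vary from 1.34 to 2.06 events per 100 patient years depending on the mean TTR values in different centers".

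**The concern.** A single power statement stands for a set of primary analyses that differ in size. Three features of the protocol make most of them smaller than the one calculated:

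- At least one INR measurement is an inclusion criterion (section 3.2.1), but 32 000 is derived without any allowance for it. The allowance appears only in the 25 600 block, which the conclusion does not mention.
- INR above 3.0 has 14 000 person-years, two thirds of the 21 000 for INR below 2.0. Section 1.1 itself links INR above 3.0 to serious bleeding, so this contrast is central to the bleeding objective.
- Splitting the cohort into new and prevalent users leaves at least one of them with no more than half the person-time.

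If the statement is carried into the report unchanged, a null result for INR above 3.0, or within one user population, may be set against a power that the analysis did not have.

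**Working it through.** **Inputs (section 4.2).** Cohort: 3 million × 1.6% × 67% = 32 160, rounded to 32 000. Person-time: 32 000 × 3 years = 96 000. Split by INR: 96 000 × 21.7% = 20 832, × 63.6% = 61 056, × 14.7% = 14 112, rounded to 21 000, 61 000 and 14 000. The significance level is not stated. Two-sided 0.05 is assumed, because the alternative is two-sided and section 4.1.1 reports "The crude and adjusted hazard ratio (HR) estimates with 95% CIs and P-values".

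**Formula.** Power = Φ(ln RR / SE − 1.96), with SE = √(1/E₁ + 1/E₂) and E = person-years × rate. The protocol does not say which group the tabulated rate belongs to, so two versions are used: (A) the same rate in both groups; (B) the tabulated rate in the reference group and rate × RR in the other. Triplets below are for RR 1.20 at 1.5, RR 1.15 at 3.0 and RR 1.10 at 6.0 per 100 person-years.

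**Step 1: reproduce the table.** For RR 1.20 at 1.5, version A: E₁ = 21 000 × 0.015 = 315 and E₂ = 61 000 × 0.015 = 915. SE = 0.0653, and 0.1823/0.0653 − 1.96 = 0.83, so power is 79.7%.

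| INR <2.0 vs 2.0–3.0 | Stated | A | B |
|---|---|---|---|
| 32 000 | 78.6/86.1/86.2 | 79.7/85.7/83.1 | 84.7/89.0/85.6 |
| 25 600 | 69.2/77.7/77.8 | 70.4/77.2/74.2 | 76.0/81.3/77.1 |

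A two-proportion approximation that treats each person-year as one trial, with the tabulated rate as the geometric mean of the two groups, matches all 36 table cells within 1.41 points. The table's arithmetic therefore stands. On its own figures the conclusion holds for 32 000, and all three cells fall below 80% for 25 600.

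**Step 2: INR above 3.0 versus 2.0–3.0.** For RR 1.20 at 1.5, version A: E₁ = 14 000 × 0.015 = 210, E₂ = 915, SE = 0.0765, 0.1823/0.0765 − 1.96 = 0.42, power 66.4%. Version B: E₁ = 252, SE = 0.0711, power 72.7%.

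| INR >3.0 vs 2.0–3.0 | A | B |
|---|---|---|
| 32 000 | 66.4/73.3/70.2 | 72.7/78.0/73.5 |
| 25 600 | 56.8/63.7/60.6 | 63.0/68.6/63.9 |

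The best-fitting approximation from step 1 gives 66.5/74.2/72.6% at 32 000. A pooled two-proportion test, which overshoots the protocol's table by up to about 6 points, gives 72/78/76%. Every version stays below 80%.

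**Step 3: the smaller user population, INR below 2.0.** The protocol does not give the split, but the smaller part has at most half: 10 500 versus 30 500 person-years of the 32 000 cohort. This takes the INR distribution and event rates to be the same in both populations. For RR 1.20 at 1.5, version A: E₁ = 157.5, E₂ = 457.5, SE = 0.0924, 0.1823/0.0924 − 1.96 = 0.01, power 50.5%. Version B: E₁ = 189, SE = 0.0865, power 55.9%. All three cells: A 50.5/57.1/54.1%, B 55.9/61.5/57.0%. To reach 80%, a population would need more than three quarters of the total person-time in every cell, so both cannot reach it.

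**Step 4: relative risk detectable with 80% power.** In version A, RR = exp(2.80 × SE); version B is solved numerically.

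- INR above 3.0, 32 000: exp(2.80 × 0.0765) = 1.24 at rate 1.5. Over both versions: 1.22–1.24 / 1.15–1.16 / 1.11.
- Half-size user population, INR below 2.0: exp(2.80 × 0.0924) = 1.30 at rate 1.5. Over both versions: 1.27–1.30 / 1.19–1.20 / 1.13–1.14.

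**Step 5: rates below 1.5.** For RR 1.20, INR below 2.0, 32 000: about 75–81% at 1.34, the lowest rate cited. At 0.5, an assumed rate, about 36–41%.

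**The case against.** The strongest reply is that the table is correct, both population sizes are printed directly above the conclusion, and the preceding text says which contrast was calculated. Figures of 78.6/86.1/86.2% are fairly described as about 80% or higher. Two of the three cells for 25 600 miss 80% by only about 2 points; the clear shortfall is 69.2%. The cohort is fixed and retrospective, and results come as hazard ratios with 95% confidence intervals, which show what is excluded whatever the planned power was. All of this stands, and it makes the matter one of reporting rather than design. It does not cover INR above 3.0 or the separate user populations, for which nothing is calculated.

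A reader might infer four stronger things that the document does not support:

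- *That the table is miscalculated.* It reproduces.
- *That 25 600 is the expected size.* The protocol says only that some patients may lack INR measurements; a 20% loss is a scenario, not a forecast.
- *That section 4.2 promises 80% power for rarer endpoints.* Its sentence is limited to rates of 1.5, 3.0 and 6.0. Only the Synopsis wording goes further, and no rates are given for myocardial infarction or cause-specific death.
- *That INR above 3.0 cannot show any 10–20% difference.* With version A, power at 32 000 / 25 600 is 92/85% for RR 1.20 at 3.0, and 98/96% for RR 1.10 at 16.56, the lower cited rate for total bleeding. The shortfall belongs to the effect and rate pairs named in the conclusion.

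**Conclusion.** The point holds as a statement broader than its calculation. At the named effects and rates, power of about 80% or higher applies to one of the two INR contrasts, in the pooled cohort, at the larger of the two sizes considered. Elsewhere:

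- 25 600 patients, same contrast: 69.2/77.7/77.8%, from the protocol's own table.
- INR above 3.0: about 66–73/73–78/70–74% at 32 000 and 57–63/64–69/61–64% at 25 600.
- The smaller of the new and prevalent user populations, INR below 2.0: at most about 51–56/57–62/54–57% even at 32 000. This is the largest shortfall.

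These figures rest on two-sided alpha 0.05 and on the protocol's own person-time. The last line also assumes the same INR distribution and rates in both user populations. The ranges reflect the unstated meaning of the tabulated rate.

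**What to change.** In section 4.2, say that the conclusion refers to INR below 2.0 versus 2.0–3.0 in the pooled cohort of 32 000, and put 69.2/77.7/77.8% for 25 600 beside it. Add power or the detectable relative risk for INR above 3.0 and for each user population, using the expected split. The values in step 4 of the working can serve until that split is known. In the Synopsis, replace the reference to the main endpoints with the rates and comparison actually calculated. Note there that primary outcomes rarer than 1.5 per 100 person-years, whose rates the protocol does not give, would have lower power.

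The cost is an edit to the text and one table. Sample size, endpoints and analyses stay as they are; the stated power becomes less favourable.

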5 STUDY LIMITATIONS/STRENGTHS

Finland has a well-developed population register system with tens of years of longitudinal follow-up data. The persons are identified in the registers with a unique personal identification number enabling linkage between different registers. These data has not been collected for study purposes, which may affect the quality of the data. However, these registers have been considered reliable for scientific research purposes.

Only those citizens that have been living in Finland for 12 months prior to index date will be included in the study.

No exact prescribed dosing information is available. Dosing is assumed based on the information of purchases and package sizes with defined daily doses (DDDs).

Coverage of the Prescription Register containing reimbursement information of all permanent residents of Finland is about 97%. Missing data includes relatively inexpensive packages which are not reimbursed. Fully reliable information on eg, acetylsalicylic acid use is then not available.

Medications used during hospitalizations are not available. However, based on the hospital care register the hospitalization periods can be taken into account to define gaps in the drug treatment periods.

No nationwide database about laboratory measurements is available. The laboratory data is then collected from separate local central laboratories. All laboratory values for particular patients may then not be available. Also changes in places of domicile may affect the follow-up of the patients. On the other hand, previous published surveys on the subject have not included INR follow-up to this extend.

To avoid selection bias, the cohort time (years 2007 to 2009) was chosen to avoid complication of patients switching from warfarin to newer anticoagulant medications eg, dabigatran.

6 STUDY CONDUCT

This study will be conducted in accordance with International Society for Pharmacoepidemiology (ISPE) Guidelines for Good Pharmacoepidemiology Practices (GPP) and applicable regulatory requirements.

The study protocol is written by following the Code of Conduct by the European Network of Centers for Pharmacoepidemiology and Pharmacovigilance (ENCePP), a project led by the European Medicines Agency to further strengthen the post-authorization monitoring of medicinal products in Europe by facilitating the conduct of multi-centre, independent, post-authorization studies focusing on safety and on benefit/risk. The parties involved in this study commit to adhere to the rules of the ENCePP Code of Conduct in their entirety.

All the information used in the study will be obtained without any potential harm to the patients. This study will be carried out as a retrospective register-based survey and the patients will not be contacted in any phase of the study. The study does not affect the treatment of the patients.

6.1 Ethics Committee Review and Informed Consent

6.1.1 Ethics Committee Review

The investigator must ensure that the required approvals from Ethics Committees, Independent Review Committees, Regulatory Authorities, and/or other local governance bodies are obtained before study initiation at the site.

Approval of Ethical Review Board of Hospital District of Helsinki and Uusimaa (HUS) will be requested to cover this nationwide study. Data permits will be requested from each registry holder based on the study protocol and ethical approval. (See also [Section 3.3](#))

6.1.2 Informed Consent

This study does not require that informed consent is obtained from patients.

This study will be carried out as a retrospective register-based survey and the patients will not be contacted in any phase of the study. The study does not affect the treatment of the patients.

6.2 Responsibilities within the Study

The study shall be conducted as described in this approved protocol. All revisions to the protocol must be discussed with, and be prepared by BMS.

For this particular study, BMS has deputed EPID Research to prepare and update the protocol. However, the versions of the protocol are approved by BMS.

6.2.1 Sponsor Roles and Responsibilities

Responsibilities are described in detail in the research agreement. The sponsor is in charge of reviewing and validating the protocol and the final statistical report.

6.2.2 CRO Roles and Responsibilities

The present survey is conducted by EPID Research. Only EPID Research (not BMS) will have access to the study data. Responsibilities are described in detail in the research agreement.

The principal investigator from EPID Research and co-investigators will write the study report. This report will be sent to BMS. Based on these results the investigators and medical steering committee with possible other co-authors (see Section 6.2.3) will prepare (a) scientific manuscript(s) for publication. BMS is entitled to view the final results and interpretations thereof prior to submission for publication and to comment in advance of submission as agreed in the research agreement and without unjustifiably delaying the publication.

A summary of the main results of the study, whether positive or negative, including results from prematurely terminated studies, will always be made available to the public. An abstract of the study findings will be provided through the ENCePP E-register of studies within three months following the final study report. The principal investigator may ask the ENCePP Secretariat to delay the publication of this abstract for a limited period pending response to peer-review comments. The outcome of a study will always be presented in an objective and truthful manner providing a comprehensive and accurate description of the findings. In no way shall the interpretation and presentation of the results be aimed towards any commercial, financial or personal interests.

6.2.3 External Advisory/Steering Committee

An external medical steering committee of external medical experts on the field has been established to guarantee scientific integrity and high medical impact of the study. The members of this medical steering committee will review (the versions of) the protocol and attend scientific publication writing. In addition to the investigators from EPID Research and members of medical steering committee some other academic collaborators may be invited to be a co-author of the publication(s).

6.3 Confidentiality of Study Data

The confidentiality of records that could identify patients within the database must be protected, respecting the privacy and confidentiality rules in accordance with the applicable regulatory requirement(s).

All patient data handled by the investigators will be anonymous ensuring the full data protection of patients. EPID Research will receive unidentifiable data including patient study IDs only. See [Section 3.3](#) for details.

6.4 Quality Control

The study will be conducted as specified in this protocol. All revisions to the protocol shall be properly documented as protocol amendments.

The study protocol has been written by following the Code of Conduct by the European Network of Centers for Pharmacoepidemiology and Pharmacovigilance (ENCePP 2011) that provides a set of rules and principles for post-authorization studies with regard to the best practices and

transparency, thereby promoting scientific independence of such studies. The study protocol also follows the key element of the Guideline for Good Pharmacoepidemiology Practices by International Society for Pharmacoepidemiology (ISPE 2008) and the recent draft Guidance for Industry and FDA Staff (2011) “Best Practices for Conducting and Reporting Pharmacoepidemiologic Safety Studies Using Electronic Healthcare Data Sets”.

Due to the study type (register study) on-site monitoring will not be performed.

